2.3.2 KNOWN POTENTIAL BENEFITS

There is no direct benefit to individual subjects from taking part in the research.

2.3.3 ASSESSMENT OF POTENTIAL RISKS AND BENEFITS

This study is of minimal risk to participants. It is possible that some youth may find some of the survey questions too sensitive or uncomfortable. Participation is voluntary; participants are reminded that they can stop participating at any point. Youth are provided with relevant resources at the end of each survey. The youth surveys are anonymous. That is, youth produce a self-generated personal code based on 8 nonidentifiable questions (e.g., first letter of mother's first name) to ensure responses will remain as anonymous as possible and can be matched across data collection points. No names or linking information will be connected to the surveys.

3 OBJECTIVES AND ENDPOINTS

OBJECTIVES	ENDPOINTS	JUSTIFICATION FOR ENDPOINTS	
Primary	
The primary goal of the study is to pilot test the feasibility and acceptability of the adapted Youth Empowerment Solutions intervention (Strengthening Connections for Change) compared to a control intervention (Job Skills).
	
Primary outcomes will include feasibility and acceptability. Feasibility is defined by session attendance. Attendance will be recorded at the beginning and end of each session. Attendance will be calculated as a proportion of total number of sessions attended (possible session attended #: 0-12 for youth participants and 0-9 for adult participants; possible proportion attended range: 0-1). Feasibility is defined by participant satisfaction. Participant Overall Satisfaction with Curriculum Content and Format will be assessed by researcher-generated Likert-scale items. At the end of the program, participants will be asked about how satisfied they were overall with the topics discussed and format of the program using 5-point Likert scale items. Means score will be calculated across the items (possible range: 1-5; higher score means higher satisfaction).
	
Feasibility and acceptability are crucial to assess before planning a larger efficacy trial because if the program is not feasible or acceptable, changes will need to be made prior to a large-scale RCT. Moreover, satisfaction is an important indicator of overall interest in the intervention, and whether youth found this programming engaging and relevant.
 
Operationalizing feasibility and acceptability came from stakeholder meetings about the amount of the curriculum that participants should receive to consider their participation as meaningful engagement.

Exploratory	
The exploratory objective is to assess the types of social networks and connections that youth make with the people around them, and to gather data on violence experiences and associated factors to inform a larger trial.
	
Exploratory outcomes include changes between pre-and post-intervention assessments of social network-level measures (e.g. network size, network density, mean link strength), attitudes towards violence, conflict resolution and coping, future orientation, and violence experiences.
	
The use of social network analysis techniques supports efforts to address critical gaps in our understanding of the networks of adults that youth in low-resource urban neighborhoods rely on for support across family, school, and community contexts and identifies targets for a network-based intervention to strengthen adult supports and reduce violence perpetration and victimization.

OBJECTIVES	ENDPOINTS	JUSTIFICATION FOR ENDPOINTS
		Additional exploratory measures will assess the feasibility of this data collection method and provide preliminary insights to guide a larger trial.

4 STUDY DESIGN

4.1 OVERALL DESIGN

This study design involves a two-arm cluster-randomized-controlled pilot feasibility trial conducted with adolescents ages 13-17 recruited from youth-serving community agencies in Pittsburgh, PA and their self-identified adult supports. Sites in four neighborhoods were randomly allocated to the intervention or control arm. Sites were selected based on participation as control sites in a previous cluster-randomized trial (NCT02427061). All neighborhoods in the study met criteria as socially or economically disadvantaged. Randomization was performed at the neighborhood level (i.e., cluster) to reduce risk for contamination. The randomization included 4 clusters that were assigned to experimental or control conditions. The study statistician performed this randomization such each site/neighborhood had a 50/50 chance of being assigned to intervention or control. Participants (anticipated n=50 youth, 25 adults) complete surveys prior to program implementation (baseline) and immediately following the program (end of program, EOP). Baseline surveys are completed in-person using tablets to complete the survey online. EOP surveys are also completed in-person on a tablet or remotely using survey links that are texted or emailed to participants using contact information provided with recruitment. We will also conduct semi-structured interviews with a subsample of adolescent-adult dyads in the intervention arm (n=5-8) to further assess acceptability and guide refinements for a larger effectiveness trial. Retention is facilitated by collecting detailed contact information and offering incentives for survey completion.

4.2 SCIENTIFIC RATIONALE FOR STUDY DESIGN

The proposed study leverages existing data, research infrastructure, and community partnerships from Manhood 2.0, a large community-partnered sexual violence prevention cluster-randomized trial engaged with 866 male adolescents, ages 13-19, through youth-serving agencies in twenty disadvantaged neighborhoods in Pittsburgh (CDCU01CE002528; PI: [name]). The Strengthening Connections for Change intervention leverages existing adolescent-adult relationship networks to increase social support and reduce violence perpetration and victimization among youth in urban neighborhoods. The comparison intervention is a job readiness training program which focuses on skills needed to prepare youth for entering the workforce, including goal setting, accountability, resume building, and interview preparation. Both intervention and control programs involve a curriculum divided into 12 sessions delivered once or twice a week. The design builds on existing research infrastructure, community partnerships and focuses on prevention principles, youth engagement, and opportunity for prosocial relationship development. Randomization is designed at the neighborhood level to reduce the risk of contamination.

4.3 JUSTIFICATION FOR INTERVENTION

Youth violence is pervasive and increases morbidity and mortality. Middle school-age youth in urban environments bear a disproportionate burden of witnessing and directly experiencing violence. Exposure to pervasive violence can negatively impact physical and mental health and risk behaviors, and increases risks for injury and incarceration. Strategies that leverage individual and relational assets to combat youth violence in urban environments during middle adolescence are urgently needed.

Adult connection may play a significant role in violence prevention. Supportive adult connections are an important source of social support across adolescence, conferring protection against myriad health risk behaviors, including violence. Interventions that strengthen adolescent-adult support networks offer a novel approach to youth violence prevention. Despite the importance of adolescent-adult connections, few evidence-based violence prevention programs exist for middle adolescence that foster adolescent-adult relationships. The Youth Empowerment Solutions curriculum (YES), an evidence-based violence prevention program, fosters interactions with adult volunteers and has been shown to reduce aggression and delinquency. In the YES ‘building intergenerational partnerships’ program component, youth interview and select adult volunteers without preexisting connections to join them in implementing community change projects. While youth report high satisfaction with the intergenerational partnership component, they have also identified challenges in fostering and maintaining meaningful adult connections in a short time span. The current proposal will use social network analysis methods to inform an adaptation of the YES ‘building intergenerational partnerships’ component that leverages existing adolescent-adult relationship networks to increase social support and reduce violence perpetration and victimization among middle school age youth in urban neighborhoods.

Strengthening Connections for Change (SCC) is a 12-session curriculum that is adapted from the Youth Empowerment Solutions curriculum (YES). The Strengthening Connections for Change intervention uses social network analysis methods to enhance the YES ‘building intergenerational partnerships’ component that leverages existing adolescent-adult relationship networks to increase social support and reduce violence perpetration and victimization among youth in urban neighborhoods. The adaptation that developed into SCC was originally a 9-session intervention. Based on participant and facilitator feedback through the iterative development phases, SCC was expanded into 12 sessions to allow the groups to have more time to thoroughly cover all activities in each session of the curriculum.

4.4 END-OF-STUDY DEFINITION

A participant is considered to have completed the study if he or she (1) completes the baseline survey, (2) attends either the intervention program, a 12-session curriculum (youth and adults) or the control program, a 12-session evidence-based job skills curriculum (youth only), and (3) completes the end of program survey.

The end of the study is defined as completion of the end of program survey shown in the Schedule of Activities (SoA), **Section 1.3**.

5 STUDY POPULATION

5.1 INCLUSION CRITERIA

Neighborhood Eligibility: Neighborhoods were identified based on having participated in NCT02427061 and having been randomized to the control intervention in that trial. Neighborhoods were recruited from the previous 10 sites by identifying a potential community partner who could host the program and were willing to be randomized to receive the intervention or control programming. Neighborhoods had existing programs and were considered lower income communities based on census information and school district data.

In order for youth to be eligible to participate in this study, an individual must meet all of the following criteria:

1. Ages 13-17
2. who speak English
3. are engaged with a community-based site
4. can provide contact information.

In order for adults to be eligible to participate in this study, an individual must meet all of the following criteria:

1. Identified by the adolescent participant as a key support (family, school, or community-based)
2. speak English
3. can provide contact information.

5.2 EXCLUSION CRITERIA

Any youth who meet any of the following criteria will be excluded from participation in this study:

1. Current involvement in the juvenile justice system.

Any adult who meets any of the following criteria will be excluded from participation in this study:

1. Non-English speaking

5.3 LIFESTYLE CONSIDERATIONS

N/A

5.4 SCREEN FAILURES

Participants who assent in the program but do not meet eligibility criteria are invited to return when they meet criteria. Examples include interested youth who are currently involved in the juvenile justice system and youth who are not yet 13 years old.

5.5 STRATEGIES FOR RECRUITMENT AND RETENTION

Youth Recruitment: In each of the participating neighborhoods, we have relationships with churches, libraries, youth serving agencies, and schools to assist with recruitment of eligible youth via flyers and word of mouth. We will draw on existing youth-serving agencies to assist with recruitment. As in previous studies, we will use 'respondent driven sampling' for youth to invite peers to participate. The type and effectiveness of strategies used for recruitment and retention will be tracked as part of the feasibility evaluation. The research assistant (RA) and the community liaisons will work with the community partners at each designated site to ensure that the parental information letter and assent forms are distributed to youth and families.

Adult recruitment: During program session #1, youth in the intervention group will be asked to identify a key adult support in his/her family, school, or community context to participate in the program. Youth will be asked to provide the identified adult with a letter from the study team that describes the research and get verbal permission to contact their key adult support. Once verbal permission is provided, the study team will reach out to the adult to facilitate enrollment using a preferred method of communication provided by the youth.

Participant Retention:

An advantage of conducting this study in Pittsburgh is that the turnover of youth in neighborhoods and schools is relatively low (except for youth who are juvenile justice involved, who will be excluded from the proposed study) and few students move out of the Pittsburgh area. As a stakeholder-engaged community-based study with strong buy-in from community agencies, stakeholders will assist with identifying and locating participants who need to complete post-intervention surveys and facilitating survey administration in community-based settings to improve retention.

The intervention will be evaluated utilizing all available data from participating youth and adults receiving the SCC curriculum or the control curriculum and completing pre-intervention and/or post-intervention surveys. We recognize retention can be a challenge; our team has experience with maintaining high retention in community intervention studies through a detailed contact sheet collected at baseline, scheduled follow up calls and emails, and working with community partners to help find youth. A system of escalating incentives for youth and adult participants will be employed. Youth will receive \$15 for completing the baseline survey, \$5 for completing each of the 12 feedback sessions, and \$20 for completing the survey after program completion (total \$95). Adults will receive \$15 for completing the baseline survey, \$5 for completing each of the 10 feedback sessions, and \$20 for completing the survey after program completion (total \$85). Even participants who may have missed portions of the sessions will still be asked to complete the post-intervention survey, utilizing an 'intent to treat' design.

6 STUDY INTERVENTION(S) OR EXPERIMENTAL MANIPULATION(S)

6.1 STUDY INTERVENTION(S) OR EXPERIMENTAL MANIPULATION(S) ADMINISTRATION

6.1.1 STUDY INTERVENTION OR EXPERIMENTAL MANIPULATION DESCRIPTION.

This pilot community-partnered cluster-randomized trial will examine the feasibility and acceptability of a social network-based youth violence prevention program called Strengthening Connections for Change for youth ages 13-17 and their self-identified key adult supports to focus on leadership, strengthening intergenerational networks, community engagement, and violence prevention. The study will be located in four lower resource Pittsburgh, Pennsylvania neighborhoods ('clusters') randomized to receive either the Strengthening Connections for Change program (i.e. intervention neighborhoods) or to a job skills training program (i.e. control neighborhoods). Randomization will occur 1:1 at the site level (2 intervention and 2 control sites). The study team will then work with each community-based site to recruit youth already engaged with the respective community site into the program to which each site has been randomized. The Strengthening Connections for Change intervention will be delivered weekly by research staff in twelve 2-hour sessions at community sites. The first 2 sessions will include youth-specific programming. For session 3-12, youth and adults will participate in separate programming for the first hour, then participate in a joint session.

Strengthening Connections for Change uses a group discussion format with activities that explore identity, adolescent-adult relationships, social networks, and community engagement. Youth invite their self-identified key adult supports to jointly participate in programming and curriculum includes youth-focused, adult-focused and jointly focused activities designed to build leadership skills, enhance intergenerational networks, challenge attitudes towards violence and retaliation, and reduce violence involvement. Strengthening Connections offers leadership development coupled with strengths-based youth violence prevention programming. The Strengthening Connections for Change curriculum will include: 1) a social network mapping session for youth to define and reflect upon existing sources of support, as well as leadership and community engagement training; 2) a curriculum for key adult supports focused on the protective effects of adult supports, key barriers/facilitators to helping youth build their support networks, and developing action steps; 3) joint sessions to address attitudes towards violence, strategies to promote network expansion and cohesion, interview and photovoice methods, and a youth-led change project. *The 12-session curriculum will be delivered over 6-12 weeks.*

The control intervention (Job Skills) uses a group discussion format to learn specific skills to prepare for employment including developing goals, seeking jobs, preparing for interviews, adapted from the widely used program called "Jump Start Success Work Readiness and Career Exploration Training" (http://www.youthworksinc.org/jumpstart_success/index.html). Discussions include a wide range of topics related to career exploration and job readiness. The Job Skills curriculum focuses on the skills needed to prepare youth for entering the workforce, including goal setting, accountability, resume building, and interview preparation. *The 12-session curriculum will be delivered over 6-12 weeks.*

All youth and adult participants will complete pre- and post-intervention surveys. Participants will be sent a text or email (based on preference) with a link to the survey, session reminders, and follow-up reminders to complete surveys before or after each group session. Participants who miss a session will also be sent a follow-up message. Dyads from the iterative testing and a subsample of 5-8 dyads from the pilot feasibility trial will also be invited to participate in a semi-structured dyadic interview, expected to last 45 minutes, following program completion.

Surveys: Youth and adult participants will be asked to complete pre- and postintervention surveys that cover a range of topics on social networks, adolescent-adult connections, attitudes towards violence, and violence involvement. A subsample of 5-8 adolescent-adult dyads will also be invited to complete a semi structured interview following program completion. Interviews will be audio-recorded. Surveys will

be offered in English using REDCAP. Paper surveys will be available as back-up in case of computer malfunction. Study staff will provide participants with instructions on using the web-based survey tool and will be available to guide participants through survey completion as needed. Participants enter their responses directly onto the tablet computer. Surveys take approximately 30-45 minutes to complete. Analogous to study procedures for Manhood 2.0, adolescent participants will produce a self-generated personal code based on eight nonidentifiable questions (e.g., “Please enter the first letter of your mother’s first name or select N/A if you don’t know or this is not relevant to you.”) to ensure responses will remain as anonymous as possible. A similar personal code will be created for adult participants that will allow linking of adult participant data to the corresponding youth’s data.

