6.3 MEASURES TO MINIMIZE BIAS: RANDOMIZATION AND BLINDING

Assignment of Interventions: Randomization was performed at the neighborhood level. The initial randomization included 4 community-based sites. The study statistician performed this randomization as a one-to-one randomization between control and intervention arms.

Randomization was performed after approval for the study was obtained for a site in a new neighborhood so that the randomization assignment would not influence a site’s willingness to participate. Sites chosen for the program have participated in other studies and interventions prior to the implementation of SCC, so many of the sites and facilitators were familiar with the content and programming guidelines. Due to the study design, investigators, research staff, participants, facilitators, and community partners could not be blinded to intervention assignment.

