8 STUDY ASSESSMENTS AND PROCEDURES

8.1 ENDPOINT AND OTHER NON-SAFETY ASSESSMENTS

Assent and Consent

Youth ages 13-17 receive a description about the research study and parental letter about the study from the community sites. The parent letter includes an option for parents/caregiver to decline their child's participation. We received a waiver of parental permission and waiver of signed consent from the University of Pittsburgh Human Subjects Research Protection Office. Research assistants review the verbal consent form with youth at the beginning of the first session and answer any questions pertaining to confidentiality, the program flow, and survey time points. The consent form covers all research surveys over the course of the program. An additional consent is used for the optional interview portion at the end of the project.

Data Collection

There are several points of data collection throughout the study including baseline surveys, feedback forms, End of Program (EOP) survey, and interview. The surveys are all anonymous, linked by a personal secret code that youth create by answering a series of questions that only they know the answer to at the beginning of each survey. This method of using a personal study code was selected to ensure anonymity and increase the likelihood of honest responses. In addition to survey data, other sources of data for this study (primarily for process evaluation and assessing intervention fidelity) include: 1) feedback forms completed by youth after the end of each session; 2) fidelity forms completed by research assistants at each session; 3) interviews with site leads and facilitators; 4) interviews with youth.

Main Study Phase

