Baseline survey: Youth are asked to complete the baseline survey the first time they attend a session (can enter study at Sessions 1 – 3; if participant is interested in joining after session 3, they are asked to return for the next round). All sites conduct web-based surveys (back up paper surveys are used as needed) on tablets using REDCap, an online data management and survey system. Responses to the anonymous web-based secure survey are entered by the youth participants themselves on an electronic tablet; no data are stored on the computers themselves. Only research staff who have been added to the project can access this online database. Data are downloaded and stored on a password-protected share drive that can only be accessed by users with the appropriate permissions. No names are connected to the survey data as each participant creates their own secret code as described above.

End of program survey: At the end of the program, youth are asked to complete an end of program survey that asks about which sessions they attended, their impressions of the program, and reassesses measures collected on the baseline survey. Surveys are self- administered on electronic tablets provided by the research staff (back up paper surveys will be used if tablets are not available or fail). All participants, regardless of the amount of curricular content completed, are eligible to take this survey; participants are asked to complete the end of program survey later if they miss the last session.

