9.4 STATISTICAL ANALYSES

9.4.1 GENERAL APPROACH

Descriptive statistics will characterize participants' demographics and baseline survey responses. T tests, Wilcoxon rank sum tests, and chi square tests will assess for differences in baseline characteristics and baseline survey responses among intervention versus control participants, after accounting for clustering. Feasibility and acceptability will be the primary outcomes of the pilot trial. Both feasibility/acceptability

and exploratory outcomes will be estimated within each study arm using point estimates and 95% confidence intervals. We will examine these endpoints separately for youth and adults. As an exploratory measure, we will assess outcomes on the difference between pre- and post-intervention measures of social network metrics, relationship quality and communication, attitudes towards violence, conflict resolution and coping, and future orientation between intervention and control participants. We will utilize generalized linear mixed models to account for site-level clustering. Missing data will be managed with multiple imputation if the mechanism of missingness is ignorable. Interview transcripts will be coded and analyzed by two independent reviewers through content analysis to identify themes related to intervention acceptability and satisfaction.

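### Youth are recruited, assented and surveyed at baseline after their site's arm is known, so the exploratory between-arm youth comparisons are open to selection at enrolment

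*Combined protocol and SAP*

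**What the plan says.** Section 6.1.1 gives the order of events. Four sites are randomised 1:1, and the study team then works with each site to "recruit youth already engaged with the respective community site into the program to which each site has been randomized". Section 5.5 adds flyers, word of mouth, local agencies and invitations from peers as recruitment routes.

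Section 6.3 states that "investigators, research staff, participants, facilitators, and community partners could not be blinded to intervention assignment". It also says that a site was randomised only after approval had been obtained for it, "so that the randomization assignment would not influence a site’s willingness to participate".

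Section 8.1 places the youth-level steps after that. "Research assistants review the verbal consent form with youth at the beginning of the first session", and this review covers how the program runs. On the baseline survey: "Youth are asked to complete the baseline survey the first time they attend a session (can enter study at Sessions 1 – 3"). A youth who wants to join after that is asked to wait for the next round.

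On analysis, sections 9.3 and 9.4.2 estimate the primary outcomes (attendance and satisfaction) within each arm. Section 9.4.1 adds exploratory comparisons of pre-post differences in a list of measures that ends with "future orientation between intervention and control participants". Section 9.4.9 adds violence perpetration and victimisation, and tests each outcome at 0.10 without multiplicity correction. For imbalance, section 9.4.1 tests baseline characteristics and survey responses between arms allowing for clustering, section 9.4.5 considers imbalanced demographics as covariates, and section 9.4.9 includes covariates that it does not name.

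**The concern.** In a cluster trial, randomising sites protects the comparison of youth only if the decision to enrol does not depend on the arm. Here each youth decides, and each recruiter invites, with the arm known. One program is violence prevention and leadership work with an invited adult; the other is employment preparation for youth alone. Youth who volunteer for one may differ from those who volunteer for the other in age, motivation or exposure to violence. SCC youth can also answer the baseline violence and attitude items knowing what their program is for.

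At stake is the reading of the exploratory contrasts, which section 2.1 wants as preliminary insight for a larger trial. A difference in change could reflect who enrolled rather than what the program did. Any side-by-side reading of attendance or satisfaction has the same weakness. The objective in section 3 invites such a reading by setting SCC against a control.

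**Working it through.** **Step 1: which steps are protected.**

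| Step | Timing relative to allocation | Protection stated |
|---|---|---|
| Site agrees to take part | Before (6.3) | Yes, by timing of randomisation |
| Youth recruited | After (6.1.1) | None |
| Youth assent | After, at first session (8.1) | None |
| Baseline survey | After, at first session attended, up to Session 3 (8.1) | None against knowledge of the arm; anonymity favours candid answers |

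The text provides no recruiter blind to arm, no arm-neutral wording and no baseline before disclosure.

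**Step 2: the plan's own precision figure.** Section 9.2 gives a within-arm margin of error of at most 0.20 with 25 youth. For a proportion of 0.5, 1.96 × sqrt(0.25/25) = 0.196. The figure reproduces with youth treated as independent, and it is not in dispute here.

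**Step 3: would the baseline comparison show an imbalance?**

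Inputs from the plan: 25 youth per arm (9.2) and two sites per arm (6.1.1), so 12.5 youth per site on average. Assumptions, because the plan gives no values: an imbalance of 0.3 to 0.5 SD on a baseline score, an ICC of 0.05 and a two-sided 5% test.

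- Ignoring clustering: SE = sqrt(2/25) = 0.283 SD. Noncentrality is 0.3/0.283 = 1.06 and 0.5/0.283 = 1.77. With 48 df (critical t 2.01), the chance of a significant result is 18% and 41%.
- With clustering: design effect = 1 + 11.5 × 0.05 = 1.575, so SE = sqrt(0.08 × 1.575) = 0.355 SD. Noncentrality is 0.3/0.355 = 0.85 and 0.5/0.355 = 1.41. With 4 − 2 = 2 df (critical t 4.30), the chance is 8% and 14%.

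The baseline comparison would therefore miss an imbalance of this size more often than not.

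**Step 4: what an outcome shift would do.** Suppose a shift of 0.3 to 0.5 SD carried into an analysed change score with no program effect. The same method at the planned 0.10 level rejects 28% to 54% of the time ignoring clustering, and 16% to 25% with 2 df. This is conditional: a difference in baseline level need not carry into change.

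**The case against.** The strongest objections are these.

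- **Different uptake is not shown.** A reader might infer that the two programs do draw different youth. The documents do not support that: the flyer, parent letter and consent script are not in the text reviewed, and section 6.1.1 draws on youth already engaged with the site, which narrows self-selection. This stands. The point is a risk.
- **The primary results are not between-arm tests.** A reader might infer that the feasibility and acceptability results are biased. Sections 9.3 and 9.4.2 estimate them within arm, so they remain valid as descriptions of those who enrolled. This stands, and limits the point to the exploratory contrasts and to informal comparison of the arms.
- **The plan already deals with imbalance.** This is partly true. The covariate rule in 9.4.5 names demographics only, the covariates in 9.4.9 are not named, and screening by test is weak at this size.
- **The detection figures do not measure bias.** This is correct. They are the chance of seeing an assumed imbalance, and the small sample and four clusters would make it low under any recruitment order.
- **Randomisation offered little here anyway.** Two-against-two allocation has only 6 possible assignments, so it would be too strong to say that good balance has been lost. That is still no reason to leave an avoidable source of selection open.
- **Concealment could disturb attendance.** Youth who join before knowing the program may leave once told. This stands and has to be carried into the fix.

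**Conclusion.** The concern holds as a risk. Recruitment, assent and baseline survey all follow open allocation, and the one stated safeguard stops at the site. The exploratory between-arm comparisons of change, and any side-by-side reading of attendance or satisfaction, are therefore not fully protected by randomisation. The mitigation in 9.4.1, 9.4.5 and 9.4.9 is partial: an imbalance of 0.3 to 0.5 SD would be seen 18% to 41% of the time ignoring clustering, or 8% to 14% at 2 df. Those figures rest on the assumed imbalance and an assumed ICC of 0.05, neither of which the plan gives. The size of any bias in change scores cannot be derived from the documents. A change is worthwhile because it is cheap and because the contrasts are meant to guide a larger trial.

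**What to change.** **Recruitment and baseline (5.5, 6.1.1, 8.1).** Use the same recruitment material, parent letter, peer-invitation text and consent wording at all four sites. Describe both programs and say that each neighbourhood receives one of them by chance. Have each youth complete the baseline survey at the first session attended before being told which program the site runs, and move the site-specific part of the consent discussion to after that survey.

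**Analysis (9.4.9).** Include the baseline value of each outcome as a covariate. Present between-arm contrasts as descriptive and open to selection at enrolment.

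**Reporting.** Give the numbers approached, eligible and enrolled by site. Sections 2.1 and 5.5 already track recruitment and enrolment, so this is a small addition.

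**Cost.** Text must be reworded and the IRB notified; no staff or visits are added. Concealment will be imperfect: site partners know the arm, and peers joining at Session 2 or 3 may have heard which program is running. Some youth may leave after disclosure, which would lower attendance for reasons unrelated to the program as normally offered. Report such early departures separately when attendance is read as feasibility.
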